## Document Change History

---

Version	Originator	Description of Change(s)	Date
1.0	[REDACTED]	Original Protocol	21-May-2021

## Overall Synopsis of the Clinical Investigation Plan (Protocol)

Sponsor Address:	CooperVision, Inc [name]
Funding Source:	CooperVision, Inc
Investigation Site:	Clinical Optics Research Lab (CORL) Indiana University School of Optometry [name]
Principal Investigator:	[REDACTED] [REDACTED] Indiana University School of Optometry [name] [REDACTED] [REDACTED]
Protocol Synopsis:	This protocol outlines the procedures that will be executed in this study
Planned Start Date	Anticipated June-July 2021
Estimated Duration	Approx 2 months
Primary Study Objective	To validate the clinical performance of the [REDACTED] daily disposable (DD) soft contact lens against the [REDACTED] DD lens
Overview of Study Design	This will be a prospective, double-masked (investigator and subject), randomized, two day crossover study comparing the Test lens against an appropriate comparator (Control) lens. Each subject will wear the [REDACTED] Test and [REDACTED] Control lenses bilaterally for two days each in random order.
Primary Outcome(s)	Comfort
Secondary Outcome(s)	Vision Lens fit Lens handling Anterior ocular health
Visit Schedule	Visit 1 - Baseline/Dispensing Pair 1 Visit 2 - Assessment of Pair 1 and Dispensing Pair 2 Visit 3 - Assessment of Pair 2 & Exit
Study Products	[REDACTED] (Test) and [REDACTED] (Control)
Subject Population	# of subjects: Maximum 50 subjects (45 to complete)
Inclusion/Exclusion	Main Inclusion criteria: As per section 7.3.1 below Main Exclusion criteria: As per section 7.3.2 below

## 1 Study Objective

---

This is a confirmatory Design Validation study to provide supportive evidence to demonstrate that the [REDACTED] lens meets the clinical performance requirements specified in the User Requirements Design Inputs per D28298, DHF0122.

Specifically, the User Requirements to be evaluated in this clinical study are:

- Vision of [REDACTED] is equivalent to [REDACTED]
- Comfort of [REDACTED] is equivalent (or better) to [REDACTED]
- Lens fit of [REDACTED] is equivalent to [REDACTED]
- Lens handling of [REDACTED] is equivalent to [REDACTED]
- Ocular health of [REDACTED] is equivalent to [REDACTED]

Details of the statistical hypothesis that are required to be met in fulfilment of Validation can be found in Section 9.1 below.

## 2 Study Design

---

This will be a prospective, two-day, double-masked (investigator and subject), randomized, bilateral crossover study comparing the Test lens against an appropriate comparator (Control) lens. Each subject will wear either the [REDACTED] lens or the [REDACTED] comparator lens (Control) in a bilateral fashion for two days followed by the alternate lens for two days. The [REDACTED] lens is a currently marketed product that is representative of the state-of-the art of contact lenses.

There will be a total of three visits in the study as described in 7.5 below

## 3 Study Devices and Comparator Products

---

### 3.1 Contact lenses

---

A summary description of the Test and Control lenses to be used in the clinical study are shown in Table 1. The Test lens is an investigational silicone hydrogel lens, with a slight modification to a contact lens material and design currently approved / cleared in the EU only [rioofilcon A/[REDACTED]. The Control lens is also an investigational lens, currently approved / cleared in the EU only.

Further details regarding the investigational lens is described in the Investigator Brochure.

**Table 1: Study lenses**

	Test Lens	Control Lens
Device Name	[REDACTED]	[REDACTED]
Regulatory status	Investigational	Investigational
Manufacturer	CooperVision, Inc	CooperVision, Inc
Material	rioofilcon A (+ DAB)	rioofilcon A
Water Content (%)	58	58
Base curve (mm)	8.60	8.60
Diameter (mm)	14.10	14.00
Power range (D)	-1.00 to -6.00	-1.00 to -6.00
Label	Investigational [Masked]	Investigational [Masked]

### **3.1.1 Intended Use**

In this clinical investigation, the study lenses are intended to be used as a single use soft contact lens. Single use lenses will be used for a maximum of one day of lens wear.

### **3.1.2 Storage of Lenses and Lens Care Solutions**

The study materials must be stored in a secured area. All lenses and lens care solutions should be stored at controlled room temperature (59-86°F).

## **3.2 Adjunct Products**

---

### **3.2.1 Contact Lens Care Products**

No contact lens care is required for this study as lenses are to be worn for a single day only. No contact lens wetting drops will be used during this study.

### **3.2.2 Other**

No other medical devices will be used in this study.

## **4 Justification for the Study Design**

---

The Apollo lens has successfully passed the preclinical biocompatibility tests as identified in the risk assessment document. Preliminary safety and clinical performance of the [REDACTED] lens have been evaluated in one feasibility clinical study. This study is summarized in the Investigator Brochure (IB).

A two-day crossover study is sufficient to validate the clinical performance of the lens against the User Requirements. A crossover design has been chosen since it minimizes the impact of potential sympathetic effects between the two eyes (e.g. an uncomfortable lens in one eye may impact the subjective rating of the fellow eye). The study contact lenses do not alter the physiology of the eye and hence there is no carryover effect requiring a washout period. The order effect will be tested.

The choice of comparator product was made in order to assess the clinical performance against a currently marketed product representative of generally accepted state of the art.

The choice of study design was made to demonstrate statistical equivalence to the comparator (Control) lens over two days of lens wear. A sample size determination was made of sufficient magnitude so as to be able to adequately test the primary statistical hypothesis, and is shown in Section 9.2.

## **5 Benefits/Risks of Study Device(s) and Study Procedures**

---

### **5.1 Anticipated Clinical Benefits**

---

There might not be direct benefits to the subjects in this study, however participation in a new study may contribute to scientific research information that may be used in the development of new contact lens products. In addition, subjects will receive an examination of the front of their eyes and may have the opportunity to try a different type of soft contact lens and/or different lens care products at no cost to them.

### **5.2 Anticipated Adverse Device Effects**

---

Ocular complications that may occur during the wearing of contact lenses include discomfort, dryness, aching or itching eyes, excessive tearing, discharge, hyperemia and variable or blurred vision. More serious risks may include photophobia, iritis, corneal edema or eye infection. Although contact lens-related infections are very infrequent, the possibility does exist. The incidence of infection due to daily-wear soft lenses is 0.035%. Almost always an infection will occur only in one eye. This risk is assumed by 35-million Americans who currently wear contact lenses.

### **5.3 Risks Associated with Participation in the Clinical Investigation**

---

This is considered a non-significant risk study based on United States Food and Drug Administration (FDA) and International Standards Organization (ISO) guidelines due to the daily wear nature of the study. The risks associated with the investigational contact lenses have been estimated in accordance with ISO 14971. A synopsis of pre-clinical and prior clinical testing results are included in the Investigator's Brochure. Risk controls to reduce the risk as far as possible have been implemented and any residual risks will be further mitigated through close evaluation by the investigators under this clinical protocol and communicated via informed consent.

### **5.4 Risks of Clinical Procedures to be Utilized in the Study**

---

Routine, non-invasive procedures will be conducted in this study. Routine clinical procedures include auto-refraction, auto-keratometry, visual acuity, anterior ocular health assessment, and contact lens fitting will be used. In addition, standard research procedures such as high magnification imaging of the lens fit may be made using 35 mm or digital cameras, in vivo confocal microscopy, and/or specular microscopy.

### **5.5 Possible Interactions with Concomitant Medical Treatments**

---

The use of contact lenses can interact with concomitant topical, ocular and/or systemic medical treatments, therefore only healthy subjects who are not currently taking concomitant medical treatments will be included in this study. Only those products approved for the use with contact lenses can be used according to their indication under this protocol.

### **5.6 Steps That will be Taken to Control or Mitigate the Risks**

---

The following Information for Safety for contact lens wear during the clinical study will be reviewed with each subject:

Hands should be washed and dried prior to touching the lenses for insertion or removal. If inserting the lenses yourself, they should be checked for tears and/or whether they are inside out prior to insertion. Eye rubbing should be avoided. Contact lenses should never be worn while swimming or in any other hazardous environment. The contact lenses are not to be slept in during the study or worn overnight and are to be replaced with a new pair according to the study lens wear schedule.

## **5.7 Rationale for Benefit-Risk Ratio**

---

The knowledge gained from this confirmatory Validation study may lead to important conclusions regarding the ocular response and performance of new contact lens materials and designs. The potential risks for participating in this study are minimal, therefore the benefit-risk ratio is acceptable.

## **6 Ethics Review / Statement of Compliance**

---

### **6.1 Relevant Standards / Guidelines**

---

This study was developed in accordance with 21 CFR Part 812 Investigational Device Exemptions [or local regulations] and the good clinical practice (GCP) principles and ethical considerations of ISO 14155 Clinical Investigation of Medical Devices for Human Subjects and Declaration of Helsinki. The detailed descriptions of ocular Adverse Events details and the biomicroscopy grading scales are adapted from ISO 11980 Ophthalmic Optics – Contact lenses and lens care products – Guidelines for clinical investigations.

### **6.2 Institutional Review Board**

---

This study will be conducted in accordance with Institutional Review Board regulations (U.S. 21CFR Part 56.103) or applicable IEC regulations. Copies of all IRB/IEC correspondence with the investigator/Sponsor will be kept on file.

This study will adhere to a protocol and informed consent document approved by the Institutional Review Board at Sterling IRB.

Address:

Sterling Institutional Review Board  
[name]  
[name]  
[contact]

### **6.3 Informed Consent**

---

Informed consent shall be obtained in writing from the subject and the process shall be documented before any procedure specific to the clinical investigation is carried out.

## 6.4 Clinical Trial Registration

---

This Study will be registered with ClinicalTrials.gov in accordance with Section 801 of the Food and Drug Administration Act (FDAA) which mandates the registration of certain clinical trials of drugs and medical devices.

# 7 Design of the Clinical Investigation

---

## 7.1 Study Endpoints

---

The primary endpoint is:

- Comfort

The secondary endpoints are:

- Vision
- Lens fit
- Lens handling
- Anterior ocular health

## 7.2 Clinical Site

---

The clinical site was selected based on the availability of representative population of subjects and Investigator's clinical research experience.

The Investigators will be required to fulfill the following criteria:

- Trained and experienced in the conduct of clinical research
- Willingness to follow the study protocol
- Trained in Good Clinical Practice (GCP) and the study protocol prior to commencing the study.

## 7.3 Subjects

---

A maximum of 50 subjects will be enrolled in this study in order for approximately 45 to complete the study. Each subject will be given a unique ID number. ID numbers will not be re-used. All subjects must meet the study inclusion and exclusion criteria listed below.

### **7.3.1 Inclusion criteria**

A person is eligible for inclusion in the study if he/she:

- Has had a self-reported oculo-visual examination in the last two years.
- Is at least 18 years of age and has full legal capacity to volunteer.
- Has read and understood the information consent letter.
- Is willing and able to follow instructions and maintain the appointment schedule.
- Is an adapted soft contact lens wearer, having worn contact lenses for a minimum 4 weeks prior to the study
- Has spectacle cylinder  $\leq 1.00\text{D}$  in both eyes.
- Has spherical contact lens power requirement between  $-1.00\text{D}$  and  $-6.00\text{D}$  in both eyes.
- Has manifest refraction visual acuities (VA) equal to or better than logMAR equivalent of 20/20 in each eye.
- Wears CLs in both eyes (monovision acceptable, but not monofit)
- Has clear corneas and no active ocular disease.
- Has not worn lenses for at least 12 hours before the examination
- Is willing to wear the study contact lenses for a minimum 8 hours on at least two consecutive days for each study pair.

### **7.3.2 Exclusion Criteria**

A person will be excluded from the study if he/she:

- Has never worn contact lenses before.
- Has any systemic disease affecting ocular health.
- Is using any concomitant systemic or topical medications that will affect ocular health.
- Has any ocular pathology or severe insufficiency of lacrimal secretion (moderate to severe dry eyes) that would affect the wearing of contact lenses.
- Has persistent, clinically significant corneal or conjunctival staining using sodium fluorescein dye.
- Has any clinically significant lid or conjunctival abnormalities, active neovascularization or any central corneal scars.
- Is aphakic.
- Has undergone corneal refractive surgery.
- Is participating in any other type of eye-related clinical or research study.

## 7.4 Procedures to Minimize Bias

---

### 7.4.1 Labelling and Masking

The Test and Control lenses will be labelled with investigational labels, according to local regulations where the clinical study is being conducted. The investigational labels will also include lens coding in order to facilitate investigator masking.

#### Decoding/Masking Procedures:

The Principal Investigator will be provided, prior to commencing the study, with the masking codes in a sealed envelope and decoding/demasking procedures for use in a medical emergency or where Serious Adverse Events are considered to be related to the Investigative or Control devices.

In order to mask the investigators, where possible, the investigator who is involved with lens insertion will be different than the investigator involved with the lens assessments.

### 7.4.2 Randomization procedures

In this crossover study design, each subject will wear the Test lens or the Control lens first in a bilateral fashion followed by the alternate lens. The order of lenses will be determined by a predetermined randomization schedule.

## 7.5 Visit Procedures

---

### 7.5.1 Visit 1a - Baseline Visit

#### Procedures to be Performed

The following evaluations will be performed to assess eligibility according to the Inclusion and Exclusion Criteria at the baseline visit only:

- The subject is expected to attend the baseline visit not wearing their habitual contact lens products.
- The subject will be required to read and sign an Informed Consent Form prior to enrolment. When the subject has signed the consent form, the subject will be considered to be enrolled in to the study.
- Auto-Refraction and Auto-Keratometry

- Sphero-cylindrical refraction will be conducted and baseline monocular and binocular High Illumination High Contrast (**HIHC**) and High Illumination Low Contrast (**HILC**) logMAR distance visual acuities recorded.
- Slit lamp biomicroscopy will be assessed according to the guidelines set out in the CVI Grading scales (Appendix 2).
- HVID (mm) and palpebral aperture size (mm) measurements using slit lamp oculars.
- The investigator will confirm that the subject satisfies the criteria set out in the inclusion/exclusion criteria.

### 7.5.2 Visit 1b: Pair 1 Dispensing Visit

*Dispensing visit should occur on same day as Visit 1a. In the event of unacceptable short-term slit-lamp findings, e.g. excessive corneal staining, Visit 1b may be conducted on a different day to Visit 1a, where slit lamp biomicroscopy should be conducted again to confirm eligibility.*

- The first study pair of contact lenses will be selected by the investigator according to the randomization table (Appendix 3) for insertion by the subjects. Subjects will be dispensed the lens power nearest to their vertex corrected refractive error requirement. The lens powers of Pair 1 and Pair 2 will be matched.
- Lenses should be allowed to settle for 10 minutes.
- An initial fit assessment will be made to ensure lens fit is acceptable (Y/N). The subject should be discontinued and exited if the lens fit is found unacceptable and the primary reason for poor fit recorded on the CRF and video footage of the fit collected.
- Monocular spherical over-refraction (SOR) will be conducted to determine if a different lens power is required.
- Monocular and binocular **HIHC** and **HILC** distance logMAR visual acuities will be recorded (SOR will be used if the subject is wearing monovision).
- Final lenses will be inserted and allowed to settle for a further 10 minutes, if applicable.
- Subjective responses will be collected per the Post-Settling Questionnaire (Appendix 4), including:
  - Lens insertion
  - Comfort satisfaction & comfort rating (6-point Likert & 100-point scales)
- A gross assessment of lens surface will be made:
  - Overall lens surface quality/wettability (acceptable / unacceptable)
  - Comments, if applicable

- Lens fit will then be assessed and graded according to the guidelines detailed in CVI Grading scales (see Appendix 2).
  - Lens centration (0.1mm steps)
  - Corneal coverage (Yes / No / Borderline)
  - Post-blink movement (0.1mm steps)
  - Mobility rating (0.50 steps)
  - Overall lens movement (-2 to +2 scale)
  - Overall lens fit acceptance and investigator reason, if unacceptable (0.25 steps). Video will be recorded in the event of poor fit.
- Information for Safety for contact lens wear during the clinical study as described in the section 5.6 will be reviewed with each subject.
- The subject must have a minimum of 8 hours of exposure in the lens on at least 2 days before their next study visit.
- The subject will be dispensed adequate lenses (including spares) to last them until the next study visit.
- The subject will be discharged and scheduled to return for Visit 2 within the required study visit window.

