## Pair 2 Dispensing

- The second study pair of contact lenses will be selected by the investigator according to the randomization table (Appendix 3) for insertion by the subjects. Subjects will be dispensed the lens power matching that of Pair 1.
- Lenses should be allowed to settle for 10 minutes.
- An initial fit assessment will be made to ensure lens fit is acceptable (Y/N). The subject should be discontinued and exited if the lens fit is found unacceptable and the primary reason for poor fit recorded on the CRF and video footage of the fit collected.
- Monocular and binocular **HIHC** and **HILC** distance logMAR visual acuities will be recorded (SOR will be used if the subject is wearing monovision).
- Subjective responses will be collected per the Post-Settling Questionnaire (Appendix 4), including:

- Lens insertion
  - Comfort satisfaction & comfort rating (6-point Likert & 100-point scales)
- A gross assessment of lens surface will be made:
  - Overall lens surface quality/wettability (acceptable / unacceptable)
  - Comments, if applicable
- Lens fit will then be assessed and graded according to the guidelines detailed in CVI Grading scales (see Appendix 2).
  - Lens centration (0.1mm steps)
  - Corneal coverage (Yes / No / Borderline)
  - Post-blink movement (0.1mm steps)
  - Mobility rating (0.50 steps)
  - Overall lens movement (-2 to +2 scale)
  - Overall lens fit acceptance and investigator reason, if unacceptable (0.25 steps). Video will be recorded in the event of poor fit.
- Information for Safety for contact lens wear during the clinical study as described in the section 5.6 will be reviewed with each subject.
- The subject must have a minimum of 8 hours of exposure in the lens on at least 2 days before their next study visit.
- The subject will be dispensed adequate lenses (including spares) to last them until the next study visit.
- The subject will be discharged and scheduled to return for Visit 2 within the required study visit window.

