### 9.1 Statistical Hypothesis

---

The primary statistical hypothesis is that the comfort performance with the Test lens will demonstrate statistical equivalence to the comparator (Control) lens over two days of lens wear.

The secondary statistical hypothesis is that the vision performance with the Test lens will demonstrate statistical equivalence to the comparator (Control) lens over two days of lens wear.

*Other hypotheses:*

The lens fit performance with the Test lens will demonstrate statistical equivalence to the comparator (Control) lens over two days of lens wear.

The lens handling performance with the Test lens will demonstrate statistical equivalence to the comparator (Control) lens over two days of lens wear.

Corneal staining performance with the Test lens will demonstrate statistical equivalence to the comparator (Control) lens over two days of lens wear.

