### **9.2.2 Secondary Hypothesis**

Assuming a standard deviation of a paired difference of 0.1 logMAR, a sample size of 27 subjects provides adequate power to detect a potential paired difference of 0.05 logMAR in mean vision scores between Test vs. Control conditions for a paired t-test (alpha = 0.05).

Therefore, a sample size of approximately 45 completing subjects is sufficient for this study.

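### At Visit 1b acuity is recorded before the final-power lens goes in and is not repeated, so for subjects whose power changes the Pair 1 and Pair 2 dispensing acuities are not like for like

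*Combined protocol and SAP*

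**What the plan says.** Section 7.5.2 sets out the Visit 1b steps as a list. The first lens is chosen from the refraction: "Subjects will be dispensed the lens power nearest to their vertex corrected refractive error requirement". After settling and an initial fit check, "Monocular spherical over-refraction (SOR) will be conducted to determine if a different lens power is required". The next step is high- and low-contrast acuity: "distance logMAR visual acuities will be recorded (SOR will be used if the subject is wearing monovision". Only after that comes "Final lenses will be inserted and allowed to settle for a further 10 minutes, if applicable". The post-settling questionnaire, the surface assessment and the graded lens fit all follow the final lens. No further acuity step is listed for that visit.

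On power, Section 7.5.2 says "The lens powers of Pair 1 and Pair 2 will be matched", and the Pair 2 Dispensing part of Section 7.5.3 says "Subjects will be dispensed the lens power matching that of Pair 1". Pair 2 has no over-refraction to revise the power and no final-lens step, and Table 2 ticks over-refraction at Visit 1b only. Pair 2 acuity is taken through the lens that is dispensed.

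Section 9.1 makes vision the secondary hypothesis: "The secondary statistical hypothesis is that the vision performance with the Test lens will demonstrate statistical equivalence to the comparator (Control) lens". The hypothesis refers to a two-day wearing period. Neither Section 9.1 nor Section 9.3 names the visit or the acuity measure that tests it. Section 4 says the order effect will be tested. Section 9.3 plans a paired t-test for some comparisons between lenses, and repeated-measures ANOVA or paired analysis between visits.

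**The concern.** Every other Visit 1b outcome is recorded on the lens the subject takes home. Acuity alone is recorded earlier. If the over-refraction leads to a new power, Pair 1 acuity belongs to a lens that has just been judged to need replacing. The over-refraction is carried into the acuity reading only for monovision wearers, so other subjects whose power changes have no correction.

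The effect falls on the first period, whichever lens is worn first. Three uses of the data are exposed:

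- the Test-Control comparison of dispensing acuity, through added variance;
- the Pair 1 change from dispensing to follow-up, which would mix a change of power with two days of wear;
- the order-effect test, which could show a period difference produced by the sequence of procedures.

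**Working it through.** **Plan's own figure.** Section 9.2.2 states: "Assuming a standard deviation of a paired difference of 0.1 logMAR, a sample size of 27 subjects provides adequate power" to detect 0.05 logMAR with a paired t-test at alpha 0.05. With the noncentral t, one-sided alpha 0.05 and 80% power give n = 27 (power 81.2%). Two-sided, power at 27 is 70.6% and 80% needs 34. The figure reproduces on the one-sided reading; the plan states neither sidedness nor target power. That is a separate matter, and the 27 does not depend on this point.

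**Inputs.**
- SD of the paired difference 0.10 logMAR, planning difference 0.05 logMAR, about 45 completers: Section 9.2.2.
- Share of subjects whose power changes, f: not in the documents. Assumed 0.10 to 0.40.
- Acuity lost through the first lens, L: not in the documents. Assumed 0.05 to 0.10 logMAR, equal in all affected subjects.
- Sequence split: Section 7.4.2 gives no ratio or blocking. 23:22 is the base case, with 25:20 and 28:17 as sensitivity cases.
- Margin for TOST (two one-sided tests): the plan states none. 0.05 logMAR is assumed, with true difference 0 and each one-sided test at 0.05.

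**Formulas.**
- Period shift = f × L.
- SD with near-balanced sequences = √(0.10² + f(1−f)L² + (fL)²) = √(0.01 + fL²).
- Bias in Test minus Control = fL × (n₁ − n₂)/45.

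**Results for dispensing acuity, n = 45.** Without the artefact, SD is 0.100 and TOST power is 90%.

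| f | L | Period shift | SD | TOST power |
|---|---|---|---|---|
| 0.10 | 0.05 | 0.005 | √0.01025 = 0.101 | 89% |
| 0.10 | 0.10 | 0.010 | √0.01100 = 0.105 | 87% |
| 0.20 | 0.05 | 0.010 | √0.01050 = 0.102 | 89% |
| 0.20 | 0.10 | 0.020 | √0.01200 = 0.110 | 83% |
| 0.30 | 0.05 | 0.015 | √0.01075 = 0.104 | 88% |
| 0.30 | 0.10 | 0.030 | √0.01300 = 0.114 | 79% |
| 0.40 | 0.05 | 0.020 | √0.01100 = 0.105 | 87% |
| 0.40 | 0.10 | 0.040 | √0.01400 = 0.118 | 75% |

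The period shift is 10% to 80% of the 0.05 logMAR planning difference (0.005/0.05 to 0.04/0.05).

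**Bias in Test minus Control.**
- 23:22: 0.005 × 1/45 = 0.0001 to 0.04 × 1/45 = 0.0009 logMAR.
- 25:20: 0.005 × 5/45 = 0.0006 to 0.04 × 5/45 = 0.0044.
- 28:17: 0.005 × 11/45 = 0.0012 to 0.04 × 11/45 = 0.0098. Under simple 1:1 randomisation of 45 subjects, a split at least this uneven has probability 13.5%.

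**With a period term.** Adjusting for period removes the (fL)² part. The worst case becomes √(0.01 + 0.4 × 0.6 × 0.01) = √0.0124 = 0.111, with TOST power about 81% instead of 75%.

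**Follow-up acuity.** Visits 2 and 3 measure acuity on the worn, dispensed pairs, so the shift and added variance there are zero.

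**The case against.** The strongest reply is that the vision hypothesis concerns two days of wear, so its natural data are the follow-up acuities, which this ordering does not touch. That stands. A reader might infer that the test of the secondary hypothesis is compromised and its power cut to 75%. The documents do not support this: nothing says that dispensing acuity tests the hypothesis. Equally, nothing excludes it, which is why the power figures are conditional.

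A reader might also infer a bias for or against the Test lens. That does not follow either. The artefact attaches to the first period and nearly cancels when sequences are balanced. An appreciable bias needs an uneven split such as 28:17, which is a sensitivity case and appears nowhere in the plan.

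The assumed ranges may be high. First lenses are already chosen from a refraction normally done the same day, over-refraction is monocular so a change may involve one eye, and not every change need cost acuity. That stands, and the lower rows of the range may be nearer the truth. The monovision exception at least partly protects those subjects. The order-effect test in Section 4 could reveal a period shift, but Section 9.3 specifies no model that adjusts for one.

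Two wordings would go too far. The first lens is worn during settling, so it is not dispensed rather than never worn. That Pair 2 matches the final Pair 1 power is the natural reading of the text, but the text does not say final.

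The list could be read as unordered, but its steps depend on one another (settle, check fit, over-refract, re-insert, settle again), so staff will probably follow it as written.

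**Conclusion.** The point holds as a sequencing defect confined to dispensing acuity. It affects non-monovision subjects whose power changes at Visit 1b and makes their two dispensing acuities non-comparable. The ordering itself is plain from the text; the size is not, because it rests on assumed values of f and L and, for power, on an assumed margin and on dispensing acuity being the test variable. Within those ranges the harm is a first-period shift and added noise, with negligible Test-Control bias near balance. The primary comfort endpoint is not affected, since Pair 1 comfort is recorded after the final lens. It is worth correcting because dispensing acuity may enter the between-visit and order-effect analyses and the correction is nearly free.

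**What to change.** In Section 7.5.2, move the high- and low-contrast acuity step to follow the step that inserts and settles the final lenses, and put the CRF in the same order. In the Pair 2 Dispensing text, state that the matched power is the final Pair 1 power. The cost is reordering two list items, one added clause and a CRF check. There is no extra procedure and no change to the sample size. Naming in Section 9 the visit and acuity measure that test the vision hypothesis would close the related gap and show whether the conditional power loss could ever have applied.
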